## **3.0 OVERALL STUDY DESIGN AND RATIONALE**

### **3.1 Overall Study Design**

This is a Phase III, multicenter, multinational, randomized, active-controlled study that compares the efficacy and safety of FCM to oral iron in pediatric participants with IDA and a documented history of an inadequate response to oral iron at least 8 weeks (56 days) prior to randomization.

Participants who satisfy the inclusion requirements and no exclusionary criteria will be eligible to participate in this study and enter into a screening phase to confirm eligibility. Randomization will occur via the IRT system in a 1:1 ratio to either Group A, participants receiving FCM, or Group B, participants receiving oral iron (oral solution drops, elixir or oral tablets) up to Day 28. Randomization will be stratified by baseline hemoglobin (<10, ≥10 g/dL) and age (1 to <12 and ≥12 to 17 years).

The oral ferrous sulfate formulation received will be based on the participant's age, such that: infants and children (1 to <4 years of age) will receive ferrous sulfate drops, children (≥4 to <12 years of age) will have the option to receive ferrous sulfate elixir or ferrous sulfate tablets, and adolescents (≥12 to 17 years of age) will receive ferrous sulfate tablets. Participants who experience adverse clinical symptoms due to the oral iron during the treatment phase may have the weight-based dose of ferrous sulfate reduced from 6 mg/kg to 3 mg/kg. If the participant is receiving tablets, the dose will be reduced from one tablet taken twice daily to one tablet per day.

Once randomized, all participants will return for efficacy and safety evaluations, including adverse events and laboratory assessments, on Days 7, 14, 28, and 35. Additional pharmacokinetic sampling and analyses will be performed for participants receiving FCM on Days 0 and 7.

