### 5.2 Drug Administration/Regimen

The Principal Investigator or designee will supervise administration of the study drug to participants. Group B (Ferrous sulfate) the first dose of will be administered before the end of the Day 0 visit.

**Group A:** Group A (FCM) will receive a dose of FCM at 15 mg/kg to a maximum single dose of 750 mg (whichever is smaller) on Days 0 and 7 for a maximum total dose of 1500 mg. FCM will be administered as either an undiluted IV push at a rate of 100 mgs (2 mL)/minute OR in no more than 250 mL of normal saline and infused over 15 minutes.

**Group B:** Group B (Oral Ferrous sulfate) will receive an age-dependent formulation of oral ferrous sulfate daily for 28 days as follows: participants <12 years of age will receive 6 mg (elemental iron)/kg/day divided into 2 daily doses of an oral liquid formulation, either drops or elixir, and participants ≥12 will receive 2 daily doses of oral tablets. Infants and children (ages 1 to <4 years) will receive oral ferrous sulfate drops, while children (ages ≥4 to <12 years)

will have the option to receive oral ferrous sulfate elixir or oral ferrous sulfate tablets. Adolescents (ages  $\geq 12$  to 17 years) will receive an oral ferrous sulfate tablet (65 mg of elemental iron/tablet/dose) twice a day (BID). The maximum daily dose for all participants is 130 mg of elemental iron.

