### **6.3.4 Day 35 (End of Study / Early Termination)**

- Physical exam
- Vitals signs
- Hematology, chemistries, and iron indices
- Serum pregnancy test for female participants of child bearing potential
- Concomitant medications assessment
- ESA and IBD stability (if applicable)
- Adverse events assessment
- Log into IRT and enter participant as complete

The participant has completed the study after the Day 35 visit is complete. If for any reason the participant does not complete the study the Day 35 procedures should be completed prior to the participant exiting from the trial.

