### 7.0 ASSESSMENT OF SAFETY

#### 7.1 Adverse Events

Any untoward medical event experienced by a participant during the course of this clinical trial, whether or not it is related to the investigational product, at any dose, is considered an adverse event (AE).

For any laboratory abnormality, the investigator will make a judgment as to its clinical significance. If the laboratory value is outside the normal limits and is felt to represent a clinically significant worsening from the baseline value, it should be considered an adverse event and should be recorded on the Adverse Events page of the eCRF. If the laboratory value is outside the normal range, but not an adverse event, the investigator should comment on the findings (i.e., “not clinically significant” or “unchanged from baseline”) in the source documentation [laboratory report]. All laboratory values at the end of study/Day 35 that have been deemed clinical significant by the Investigator should be followed until they are back into normal range.

For the purposes of this study, non-serious anemia (Hgb or Hct below the normal range or worsened from baseline) or iron deficiency (iron indices below the normal range or worsened from baseline) will not be considered adverse events. Anemia or iron deficiency will be considered end points if an intervention is required.

To quantify the severity of adverse events, the National Cancer Institute (NCI)-Common Terminology Criteria for Adverse Events (CTCAE), Version 5 or higher should be used to grade all events. These criteria are provided in the procedure manual.

If a CTCAE criterion does not exist, the investigator should use Table 7.1.1 to assign the adverse event grade.

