### **8.5.3 Adverse Events of Special Interest**

Adverse events (AEs) of special interest include hypersensitivity, hypersensitivity-like reactions, and cardiovascular events. Hypersensitivity and hypersensitivity-like reactions will be identified using standardized MedDRA queries. Cardiovascular events will be identified using the SOCs for cardiac disorders and vascular disorders.

The overviews and summaries that are provided for all TEAEs will also be provided for the AEs of special interest. In addition, the time to onset and time to recovery will be summarized.

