### 2.3.4 Handling of Missing Data

A participant who withdraws from the study for any reason will be included in the analyses regardless of time on study. Methods for handling withdrawals and missing data will be specific to each endpoint to be analyzed. Missing data will not be imputed for descriptive statistical summaries in safety or efficacy.

For statistical inferential (models) analyses, missing data will be imputed using last observation carried forward (LOCF) method for hemoglobin and other efficacy endpoints. e.g. for primary endpoint, hemoglobin, when Day 35 data is missing (subject has discontinued before Day 35, or measurement not taken at Day 35 though subject was not discontinued), Day 28 result will be carried forward. If the post-baseline value of the first scheduled visit is missing, the worst value obtained from the same time point of all subjects in ITT population will be used for both treatment groups. The worst value is defined as the lowest value for hemoglobin, ferritin, TSAT and reticulocyte hemoglobin content.

Supportive analyses will assess the impact of missing values on inferences based on primary efficacy endpoints and missing data will be handled by using missing at random (MAR) in

mixed effect model repeat measurement (MMRM) model. The observed case will also be applied for primary analysis.

Dates missing the day or both day and month of the year will adhere to the following conventions to classify TEAE and to classify prior/concomitant medications.

- A medication with a completely missing start date will be considered a prior medication. A medication with a completely missing stop date will be considered a concomitant medication.
- If complete AE onset date is missing and AE end date is on or after the first dose date then it will be counted as a treatment emergent AE (TEAE) for the study. If complete AE onset date is missing and AE end date is before the first dose date then it will be counted as a not treatment emergent AE (TEAE) for the study.
- If an AE or a medication has a partial missing start or stop date, the following rules will be used for imputation:
  - If year is present but month and day are missing, impute start date as January 1 of that year or first dose date if the year is the same as the year of first dose date and impute stop date as December 31 of that year.

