### **7.3 CLINICAL LABORATORY PARAMETERS**

Laboratory assessments include hematology, clinical chemistry, and iron indices:

- Hematology: Hgb, Hct, RBC, WBC, MCV, MCH, MCHC, RDW, platelets, differential count, reticulocyte count and reticulocyte hemoglobin content (CHr)
- Clinical chemistry: sodium, potassium, chloride, BUN, creatinine, albumin, alkaline phosphatase, total bilirubin, GGT, AST, ALT, LDH, calcium, phosphorus, glucose, bicarbonate and magnesium.
- Iron indices: serum iron, serum ferritin, and total iron binding capacity (TIBC), and percentage serum transferrin saturation (TSAT).
- Other: Serum pregnancy test

All laboratory parameters will be presented in conventional units. The actual value and mean change from baseline to each scheduled visit will be summarized using descriptive statistics by treatment for each laboratory test group above. All abnormal laboratory values will be presented in listings.

Time course table for serum phosphate will be constructed for FCM subjects in safety population. Descriptive statistics of days to first value of specified CTC grade and days to return to normal will be summarized. Only the subjects that were under FCM treatment and had a normal serum phosphate baseline value will be included in this table.

The number and percent of subjects with treatment-emergent potentially clinically significant (PCS) laboratory values after baseline will be summarized by visit and by treatment. The denominator is all subjects with normal baseline and at least one post baseline assessment in the

safety population and the numerator is the number of subjects with PCS (i.e., meets Grade 3 or Grade 4 AE scale defined in Division of AIDS (DAIDS) Table for Grading the Severity of Adult and Pediatric Adverse Events, Version 2.1 from March 2017 (Division of AIDS, National Institute of Allergy and Infectious Diseases, National Institutes of Health, US Department of Health and Human Services)) at any post-baseline visit.

Shift from baseline AE grade to maximum post-baseline AE grade, and shift from baseline to the last visit in terms of AE grade will be summarized by treatment, separately.

The AE grade for Chemistries and Hematology are defined in Appendix 1.1. BUN, hematocrit, bands and iron indices do not have adverse event scales available and are not evaluated separately as possible AEs.

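### SAP 7.3 has no censoring rule for days to phosphate recovery, so the planned summary is insensitive to long episodes of low phosphate after FCM

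*SAP*

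**What the plan says.** SAP 7.3 sets up a serum phosphate time-course table in the safety population: "Descriptive statistics of days to first value of specified CTC grade and days to return to normal will be summarized". Its scope is limited: "Only the subjects that were under FCM treatment and had a normal serum phosphate baseline value will be included in this table". The section does not define where the interval starts (first dose or first low value). It gives no rule for a child whose phosphate never returns to normal while observed, and it asks for no count of such children.

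SAP 2.3.4 adds: "Missing data will not be imputed for descriptive statistical summaries in safety or efficacy".

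On timing, Protocol 5.2 gives FCM "on Days 0 and 7 for a maximum total dose of 1500 mg". Protocol 3.1 places the post-randomisation "laboratory assessments, on Days 7, 14, 28, and 35", and Protocol 6.4 includes phosphorus in the chemistry panel. Protocol 6.3.4 closes participation: "The participant has completed the study after the Day 35 visit is complete".

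There are two routes to later values. Protocol 7.1 says end-of-study laboratory values "deemed clinical significant by the Investigator should be followed until they are back into normal range". Protocol 6.4 lets an investigator repeat an abnormal Day 35 laboratory test after notifying the sponsor. The SAP does not say whether such values enter the phosphate table. SAP 2.3.3 restricts by-visit summaries to scheduled visits and opens shift tables to all visits, but assigns this table to neither.

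**The concern.** Days to return to normal is a right-censored quantity. A mean or median can be computed only from children with an observed return, and the SAP imputes nothing for the rest. That unrecovered children drop out is an inference from these two facts rather than a written rule, but no other reading follows from the text as it stands. The children who drop out are those whose episodes outlast their observation.

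Hypophosphatemia is a special-interest event in SAP 7.2.1, but that section lists only incidence summaries by SOC and PT. The phosphate table is therefore the only planned summary of how long low phosphate lasts in these children. If many are still low at Day 35, a reader would see a short duration and have no direct statement of how many had not recovered.

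**Working it through.** The plan gives no phosphate recovery figure, so there is none to reproduce. The first step below uses the schedule alone. The later steps rest on assumed recovery times.

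**1. Ceiling set by the visits.** From the second dose to the last scheduled phosphate is 35 − 7 = 28 days. Counted from the first low value, the longest return that a scheduled visit can record is:
- first low at Day 7: 35 − 7 = 28 days
- first low at Day 14: 35 − 14 = 21 days
- first low at Day 28: 35 − 28 = 7 days
- first low at Day 35: none

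**2. Illustration.** Assumptions: the interval starts at a first low value on Day 14; recovery is exponential with true median m, so S(t) = 2^(−t/m); return is read at the next scheduled visit; no later values are used. The only recordable durations are 14 days (Day 28) and 21 days (Day 35).

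- p14 = 1 − S(14); p21 = S(14) − S(21); unresolved U = S(21)
- resolved-only mean = (14·p14 + 21·p21) / (1 − U)
- true mean = m / ln 2

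For m = 21: S(14) = 0.630 and S(21) = 0.500, so p14 = 0.370 and p21 = 0.130. The mean is (5.18 + 2.73) / 0.500 = 15.8 days, against a true mean of 30.3.

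| True median (days) | p14 | p21 | Unresolved | Resolved-only mean | Resolved-only median | True mean |
|---|---|---|---|---|---|---|
| 7 | 0.750 | 0.125 | 13% | 15.0 | 14 | 10.1 |
| 14 | 0.500 | 0.146 | 35% | 15.6 | 14 | 20.2 |
| 21 | 0.370 | 0.130 | 50% | 15.8 | 14 | 30.3 |
| 28 | 0.293 | 0.113 | 59% | 15.9 | 14 | 40.4 |
| 42 | 0.206 | 0.087 | 71% | 16.1 | 14 | 60.6 |

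The resolved-only median is 14 in every row, because Day 28 returns are always more than half of those observed.

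**3. Other assumptions.**
- First low at Day 7 (recordable durations 7, 21 and 28 days), exponential: true medians of 14, 21, 28 and 42 days leave 25%, 40%, 50% and 63% unresolved, with resolved-only means of 16.5, 17.4, 17.9 and 18.3 days.
- First low at Day 28: every recorded duration is 7 days, whatever the truth.
- First low at Day 14, Weibull shape 2, S(t) = 2^(−(t/m)²): true medians of 21, 28 and 42 days leave 50%, 68% and 84% unresolved. Resolved-only means are 17.3, 17.6 and 17.7 days against true means of 22.4, 29.8 and 44.7.

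**4. Partial later follow-up.** Under the step 2 assumptions, an unresolved child's total duration averages 21 + m/ln 2. If half of the unresolved are followed to recovery and counted, the mean is [(14·p14 + 21·p21) + 0.5·U·(21 + m/ln 2)] / (1 − 0.5·U). For m = 21 this is (7.91 + 12.82) / 0.75 = 27.6 days. With all followed it is 7.91 + 0.5 × 51.3 = 33.6 days. For true medians of 14, 21 and 28 days the results are about 21, 28 and 35 days, against 25, 34 and 43 with all followed. The shortfall shrinks but remains.

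**5. Effect of censoring.** Keeping unresolved children at risk to Day 35 in step 2 gives a Kaplan-Meier median that is not reached (more than 21 days) for true medians of 28 and 42 days, beside 59% and 71% unresolved.

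**The case against.** **Visit spacing works the other way.** Visits 7 to 14 days apart record recovery late. With a true median of 7 days the table would overstate duration, and with a true median of 14 days the table median of 14 is not too short. This stands: understatement depends on a material share of children being unresolved.

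**Later values may exist.** A reader might infer that asymptomatic low values never have a later result. The protocol does not say so. Section 7.1 turns on clinical significance, not symptoms, and section 6.4 permits follow-up of any abnormal Day 35 laboratory value. The most marked cases may well be the ones followed. This reduces the problem, but follow-up is not required for every low value, and the SAP does not commit to using the results.

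**Some of the information appears elsewhere.** SAP 2.1 requires n with each continuous summary, so comparing the n for onset with the n for return would hint at non-recovery if both use the same threshold. SAP 7.3 also gives phosphorus by visit and lists abnormal values. None of these estimates duration. The shift-to-last-visit table does not help either, since Appendix 1.1 as reproduced has no phosphate grade.

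**It is a small descriptive table.** It is single-arm, untested and covers at most about 36 children. That limits the weight of the point but does not support a summary confined to recovered children.

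**Conclusion.** The concern holds in a conditional form. As written, SAP 7.3 gives no duration for children still low at their last value. The summary is therefore insensitive to long episodes, and it understates duration if a material share are unresolved. In the main illustration the resolved-only mean moves only from 15.6 to 16.1 days as the true mean rises from about 20 to 61 days. All recovery times are assumptions, and the documents cannot show how many children will be unresolved.

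Three stronger readings are not supported:
- That duration is understated in all cases. Short episodes are overstated by the visit spacing.
- That the table looks most reassuring when recovery is slowest. In the illustration the mean rises slightly as recovery slows; it is insensitive, not reversed.
- That the same defect extends to Protocol 8.5.3, which says "In addition, the time to onset and time to recovery will be summarized". Its special-interest list does not include hypophosphatemia, and SAP 7.2.1 carries no time-to-recovery summary to correct.

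The sponsor should correct this. It does not touch the primary endpoint, but it governs how the duration of a named safety concern in children is reported.

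**What to change.** Amend SAP 7.3 to:
- define the start of the interval, for example the first low phosphate value;
- censor children not yet normal at their last phosphate measurement;
- state that unscheduled and post-Day-35 values are used where they exist;
- report the number and percent unresolved at last measurement;
- give a Kaplan-Meier median with 95% CI, or an interval-censored estimate given the visit spacing, shown as 'not reached' where that applies.

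The cost is SAP wording and one table shell. No new data and no change in patient management are needed. The downside is precision: with at most about 36 FCM children, fewer after the normal-baseline restriction, the interval may be wide or the median not reached. A not-reached median beside the count unresolved is still more informative than a mean over recovered children only.

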### **8.5.4 Clinical Laboratory Findings**

Clinical laboratory variables will be presented in two ways. First, the mean change from baseline to each scheduled visit will be summarized. Second, the number and percent of participants with treatment-emergent PCS laboratory values will be tabulated. Treatment-emergent PCS laboratory tests are those in which the baseline value is normal and post-baseline value is abnormal (i.e., meets Grade III or Grade IV toxicity criteria from the NCI-CTC Version 5 or higher). Baseline will be defined as the last value obtained before randomization.

No formal statistical tests will be performed.

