### 1.3 SUMMARY OF THE STUDY DESIGN

#### 1.3.1 General Study Design and Plan

This is a Phase III, multicenter, multinational, randomized, active-controlled study that compares the efficacy and safety of FCM to oral iron in pediatric participants with IDA and a documented history of an inadequate response to oral iron therapy at least 8 weeks (56 days) prior to screening.

FCM injection is a stable, non-dextran, Type I polynuclear iron (III) -hydroxide carbohydrate complex developed as an intravenous (IV) iron replacement therapy for the treatment of IDA. The duration of this study is approximately 6 weeks and the number of sites is approximately 30. Participants who satisfy the inclusion requirements and no exclusion criteria will be eligible to participate in this study and enter into a screening phase to confirm eligibility. All eligible participants will be randomized in a 1:1 ratio to receive either FCM at 15 mg/kg to a maximum single dose of 750 mg on Days 0 and 7 for a maximum total dose of 1500 mg in Group A or oral iron (oral solution drops, elixir or oral tablets) twice daily for 28 days in Group B. Randomization will be stratified by baseline hemoglobin (<10,  $\geq$ 10 g/dL) and age (1 to <12 and  $\geq$ 12 to 17 years). The oral ferrous sulfate formulation received will be based on the participant's age, such that infants and children (1 to <4 years of age) will receive ferrous sulfate drops, children ( $\geq$ 4 to <12 years of age) will have the option to receive ferrous sulfate elixir or ferrous sulfate tablets, and adolescents ( $\geq$ 12 to 17 years of age) will receive ferrous sulfate tablets. If the participants experience adverse clinical symptoms due to the oral iron during the treatment phase, the weight-based dose of ferrous sulfate will be reduced from 6 mg/kg to 3 mg/kg. As for the participants who receive tablets, the dose will be reduced from one tablet taken twice daily to one tablet per day.

Once randomized, all participants will return for efficacy and safety evaluations, including adverse events and laboratory assessments, on Days 7, 14, 28, and 35. Additional pharmacokinetic sampling and analyses will be performed for participants receiving FCM on Days 0 and 7.

The Schedule of Events is presented by Table 1.

Table 1 Schedule of Events

Visit Day	Screening (Day -7 + 1)	Day 0	Day 7	Day 14	Day 28	DAY 35
Informed Consent / Assent	X					
Medical History	X					
Physical Exam		X				X
Inclusion/Exclusion Criteria	X	X				

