## 2. STATISTICAL METHODS

### 2.1 GENERAL CONSIDERATIONS

Analysis datasets will be produced according to CDISC standards. All study-collected data will be summarized in tables or graphs. Listing will be produced when appropriate and all ICH-required listings will be produced.

Continuous variables will be summarized by number of observations (n), mean, standard deviation (SD), median, quartiles (Q1 and Q3), minimum (min), and maximum (max) values. Other descriptive statistics (e.g., coefficient of variation) may be reported when appropriate. Analysis of categorical variables will include frequency counts and percentages. Unknown and missing data may be presented as a separate category and the denominator will include unknown or missing values as appropriate.

If applicable, hypothesis testing will be carried out at the two-sided  $\alpha=0.05$  level unless otherwise specified; 2-sided 95% confidence intervals (CIs) will be presented, where specified.

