### 2.3.3 Time Windows for Analysis

Assessment windows will not be defined for the purpose of classifying measurements obtained outside scheduled assessment times for safety and efficacy analyses. The summary by visit will be based on the observations at scheduled visits only. Shift tables will be based on the observations at all visits including both scheduled and unscheduled visits.

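### SAP 7.3 asks for potentially clinically significant laboratory values by visit but defines only a whole-study numerator, so read literally every visit row shows the same percentage

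*SAP*

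**What the plan says.** SAP 7.3 states that the number and percent of subjects with treatment-emergent PCS "laboratory values after baseline will be summarized by visit and by treatment". The next sentence supplies the formula. For the denominator it says: "The denominator is all subjects with normal baseline and at least one post baseline assessment", restricted to the safety population. For the numerator it says: "the numerator is the number of subjects with PCS", meaning Grade 3 or 4 on the SAP's grading scale, "at any post-baseline visit". No other numerator or denominator is given for this table.

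Three other places bear on it:

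- SAP 2.3.3, on visit summaries generally: "The summary by visit will be based on the observations at scheduled visits only".
- SAP 2.1, on categorical summaries: "the denominator will include unknown or missing values as appropriate".
- Protocol 8.5.4, which asks for the same table with no visit split: "the number and percent of participants with treatment-emergent PCS laboratory values will be tabulated".

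SAP section 9, which lists the major departures from the protocol, records the change of laboratory grading scale. It does not mention adding a visit split.

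**The concern.** A by-visit row should show how many children were abnormal at that visit. The stated numerator instead counts a child in every row once that child has been abnormal at any time, including rows for visits at which the value was normal. The denominator is also fixed for the whole study. It keeps children who have no sample at the visit in question and in whom no abnormality could have been seen there.

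The by-visit PCS table is the only planned display of Grade 3 or 4 frequency visit by visit in both arms. Ferric carboxymaltose is given on Days 0 and 7 and oral iron for 28 days, so the timing of abnormalities could differ between arms. If the rows are identical they carry no timing. If two programmers resolve the conflict differently, they will produce different tables from the same data.

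**Working it through.** The plan states no figure to reproduce. The check sets the definitions against the display, then sizes the gap.

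**Inputs.** Post-baseline laboratory visits: four, from SAP 1.3.1 ("including adverse events and laboratory assessments, on Days 7, 14, 28, and 35"). Arm size for illustration: 36, from the Protocol synopsis. Abnormality counts, sampling counts, per-visit probabilities and missing fractions are assumptions; the documents give none.

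**Step 1: do the definitions vary by visit?** The numerator refers to any post-baseline visit and the denominator to any post-baseline assessment. Neither depends on the row. The percentage is therefore one constant per analyte and arm.

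**Step 2: size of the numerator problem.** Suppose all PCS values fall at scheduled visits. A child abnormal at k of the four visits is counted 4 times across the rows under the literal rule, against a true k times. The overstatement, averaged over rows, is 4/k:

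- k = 1: 4/1 = 4
- k = 2: 4/2 = 2
- k = 4: 4/4 = 1, no overstatement

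As a second view, let each visit independently carry probability p of a PCS value. The any-visit probability is 1 − (1 − p)^4:

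- p = 2%: 7.8%, ratio 7.8/2 = 3.9
- p = 5%: 18.5%, ratio 18.5/5 = 3.7
- p = 10%: 34.4%, ratio 34.4/10 = 3.4

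Independence is unfavourable to the SAP wording. Abnormalities that persist across visits pull the ratio towards 1.

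**Step 3: size of the denominator problem.** With a visit-specific numerator over the fixed denominator, the shown rate is the true rate among sampled children × (1 − m), where m is the fraction of eligible children unsampled at that visit and the rate is 10%:

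- m = 0: 10%
- m = 10%: 10% × 0.90 = 9%
- m = 20%: 10% × 0.80 = 8%

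Equal m in both arms leaves the ratio of their rates unchanged and shrinks their difference by the same factor. The comparison tilts towards one arm only if m differs between arms.

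**Step 4: both together.** Assume 36 eligible children in one arm and seven different children with PCS, each at one visit only.

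| Visit | PCS at visit | Sampled | SAP rule, literal | Visit numerator, fixed denominator | Visit numerator, visit denominator |
|---|---|---|---|---|---|
| Day 7 | 1 | 36 | 7/36 = 19.4% | 1/36 = 2.8% | 1/36 = 2.8% |
| Day 14 | 4 | 34 | 7/36 = 19.4% | 4/36 = 11.1% | 4/34 = 11.8% |
| Day 28 | 2 | 32 | 7/36 = 19.4% | 2/36 = 5.6% | 2/32 = 6.25% |
| Day 35 | 0 | 30 | 7/36 = 19.4% | 0/36 = 0% | 0/30 = 0% |

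The numerator does almost all the damage. The Day 35 row would show 19.4% when no sampled child was abnormal. The denominator moves each row by less than one percentage point.

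**Step 5: does another section repair it?** SAP 2.3.3 selects which records enter a visit summary but defines no visit-level numerator. SAP 2.1 could at most justify the denominator. Protocol 8.5.4 has no visit rows to define.

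**The case against.** The strongest defence is that nobody would program the literal rule. Four identical rows would be noticed at table review, and SAP 2.3.3 points towards rows built from each visit's own observations, with the any-visit definition serving an overall row. That is a plausible guess at intent, but the SAP does not say it.

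A reader might go further than the documents allow in four ways:

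- *That no by-visit percentage could be right.* A visit-specific numerator over a fixed eligible set is a legitimate convention. SAP 2.1 leaves room for it, and it is exact when every eligible child is sampled at the visit.
- *That the overstatement is fourfold.* Four is the top of a range of 1 to 4, reached only if each affected child is abnormal at a single scheduled visit.
- *That the safety comparison is biased.* Under the fixed denominator that needs missingness to differ by arm, and nothing in the documents shows that it will. Protocol 6.3.4 asks for the Day 35 procedures, including laboratory samples, before an early leaver exits, which limits missing end-of-study samples. Protocol 8.5.4 plans no formal tests of laboratory data.
- *That timing is lost altogether.* SAP 7.3 also plans mean changes at each scheduled visit, listings of all abnormal values, shifts to the maximum and last grade, and a phosphate time course for the ferric carboxymaltose group. These show timing in part, though none gives Grade 3 or 4 rates by visit in both arms.

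What stands is the mismatch between a by-visit display and an any-visit numerator.

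**Conclusion.** The point holds, as a minor error in a stated rule rather than a missing detail. Followed as written, SAP 7.3 yields the same whole-study percentage in every visit row, overstating visit-specific counts by a factor between 1 and 4 on average across the four scheduled visits. Where in that range it falls depends on how long abnormalities persist, which the documents do not say. The bounds assume that all PCS values occur at scheduled visits.

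The fixed denominator is secondary. It understates a visit rate only by the fraction of eligible children unsampled at that visit.

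The any-time incidence is well defined and matches Protocol 8.5.4. The table is descriptive, and the primary efficacy result is untouched.

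**What to change.** Amend SAP 7.3 in one of two ways.

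1. Keep the visit rows. For each, the numerator is subjects with a PCS value of the analyte at that scheduled visit, and the denominator is normal-baseline subjects with a non-missing value of that analyte at that visit. Keep the present definition for one separate row covering any post-baseline visit.
2. Delete the by-visit split, so that the table reports one any-time incidence per arm as Protocol 8.5.4 asks.

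The first keeps timing in both arms; the second is simpler. Either costs about one sentence of SAP text and minor table programming, with no new data.
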